## **8.6.2. Instructions for Reporting Special Situations**

### **8.6.2.1. Instructions for Reporting Pregnancies**

The investigator should report all pregnancies that are identified after the subject first consents to participate in the study (ie, signs the informed consent) and throughout the study, including the post study drug follow-up period, to Gilead DSPH or designee using the pregnancy report form within 24 hours of becoming aware of the pregnancy. Refer to the eCRF completion guidelines for full instructions on the mechanism of pregnancy reporting.

The pregnancy itself is not considered an AE nor is an induced elective abortion to terminate a pregnancy without medical reasons.

Any premature termination of pregnancy (eg, a spontaneous abortion, an induced therapeutic abortion due to complications or other medical reasons) must be reported within 24 hours as an SAE. The underlying medical reason for this procedure should be recorded as the AE term.

A spontaneous abortion is always considered to be an SAE, and therefore should be reported as such. Furthermore, any SAE occurring as an adverse pregnancy outcome post study must be reported to Gilead DSPH or designee.

The subject should receive appropriate monitoring and care until the conclusion of the pregnancy. The outcome should be reported to Gilead DSPH or designee using the pregnancy outcome report form. If the end of the pregnancy occurs after the study has been completed, the outcome should be reported directly to Gilead DSPH.

Pregnancies of female partners of male study subjects exposed to Gilead or other drugs required on study (ofatumumab) must also be reported and relevant information should be submitted to Gilead DSPH or designee using the pregnancy and pregnancy outcome forms within 24 hours. Monitoring of the subject should continue until the conclusion of the pregnancy. If the end of the pregnancy occurs after the study has been completed, the outcome should be reported directly to Gilead DSPH.

Gilead DSPH contact information is as follows: Email: **PPD** and  
Fax: **PPD**

Refer to Section [5.5.3](#) for Pregnancy Precautions, Definitions for Female of Childbearing Potential, and Contraceptive Recommendations.

#### 8.6.2.2. Reporting Other Special Situations

All other special situations (excluding pregnancy) must be reported on the special situations report form and forwarded to Gilead DSPH or designee within 24 hours of the investigator becoming aware of the situation. These reports must consist of situations that involve study IMP, but do not apply to concomitant medications. Any inappropriate use of medications prohibited by this protocol should not be reported as “misuse,” but may be more appropriately documented as a protocol deviation.

All clinical sequelae in relation to these special situation reports will be reported as AEs or SAEs at the same time using the AE eCRF and/or the SAE report form. Details of the symptoms and signs, clinical management, and outcome will be reported, when available.

## **9. STATISTICAL CONSIDERATIONS**

### **9.1. Analysis Objectives**

As noted in Section 3.1, the primary objective of this clinical trial will be to evaluate the effect of the addition of idelalisib to ofatumumab on PFS.

As described in Section 3.2, the secondary objectives of this clinical trial will focus on determining the effect of the addition of idelalisib to ofatumumab on the onset, magnitude, and duration of tumor control; measures of patient well-being (including OS, HRQL; and changes in subject performance status); disease-associated biomarkers and potential mechanisms of resistance; treatment administration; safety; and health resource utilization.

### **9.2. Analysis Endpoints**

#### **9.2.1. Primary Endpoint**

The primary endpoint of the study is PFS, as defined in Section 3.3.

#### **9.2.2. Secondary and Exploratory Endpoints**

The secondary and exploratory endpoints of the study are defined in Section 3.4, grouped in categories relating to tumor control, patient well-being, pharmacodynamic markers of drug activity and resistance, exposure, safety, and pharmacoeconomics.

Of these endpoints, 5 endpoints are designated as secondary endpoints for which sequential testing will be performed to control Type I error rate (see Section 9.4.1.6). These secondary endpoints will be ORR, lymphadenopathy node response rate, OS, PFS in the subgroup of subjects with 17p deletion and/or TP53 mutation, and CR rate. Other endpoints will be considered exploratory.

### **9.3. Analysis Conventions**

#### **9.3.1. Analysis Sets**

##### **9.3.1.1. Intent-to-Treat Analysis Set**

The ITT analysis set includes data from all subjects who are randomized regardless of whether subjects receive any study drug(s), or receive a different regimen from that to which they were randomized. Study drug assignment will be designated according to randomization.

This analysis set will be used in the analyses of subject characteristics, PFS, ORR, OS, CR rate and health outcome variables. The analysis of PFS based on the ITT analysis set will be considered the primary analysis of the study. Subjects in the ITT analysis set who do not have sufficient baseline or on-study tumor status information to be adequately assessed for response status (ie, those with best overall responses of NE or ND) will be included in the denominators in calculations of response rates.

#### 9.3.1.2. Per-Protocol Analysis Set

The PP analysis set includes data from subjects in the ITT analysis set who meet the general criteria defining the target population for this study, are adherent to the protocol, are compliant with study drug treatment, and are evaluable for relevant efficacy endpoints. Study drug assignment will be designated according to the actual treatment received. The specific classification of subjects to be included in the PP analysis set will be included in the statistical analysis plan which will be finalized prior to database lock.

The PP analysis set will be used in sensitivity analyses of the primary and the following secondary efficacy variables: PFS, ORR, lymphadenopathy node response rate, and PFS in the subgroup of subjects with 17p deletion and/or TP53 mutation.

#### 9.3.1.3. Safety Analysis Set

A safety analysis set will include data from subjects who receive  $\geq 1$  dose of study treatment, with treatment assignments designated according to the actual treatment received.

This analysis set will be used in the analyses of safety variables as well as study treatment administration (for idelalisib and ofatumumab), and post-study therapy.

#### 9.3.1.4. Pharmacodynamic/Pharmacokinetic Analysis Sets

The pharmacodynamic/pharmacokinetic analysis sets include data from subjects in the safety analysis set who have the necessary baseline and on-study measurements to provide interpretable results for the specific parameters of interest.

These analysis sets will be used in the analyses of AKT phosphorylation, chemokines/cytokines, and idelalisib plasma concentrations.

### 9.3.2. Data Handling Conventions

#### 9.3.2.1. General Methods

By-subject listings will be created for important variables from each eCRF module. Summary tables for continuous variables will contain the following statistics: N (number in analysis set), n (number with data), mean, and standard deviation, 95% confidence intervals (CIs) on the mean, median, minimum, and maximum. Summary tables for categorical variables will include: N, n, percentage, and 95% CIs on the percentage. Unless otherwise indicated, 95% CIs for binary variables will be calculated using the binomial distribution (exact method) and will be 2-sided. Data will be described and summarized by relevant treatment arm, analysis set, and timepoint. As appropriate, changes from baseline to each subsequent timepoint will be described and summarized by treatment arm. Similarly, as appropriate, the best change from baseline during the study will also be described and summarized by treatment arm. Graphical techniques (eg, waterfall plots, Kaplan-Meier curves, line plots) may be used when such methods are appropriate and informative.

The baseline value used in each analysis will be the last (most recent) pre-treatment value. Subjects with discrepancies between the stratification factor values at randomization and the actual values as documented on data review will be categorized in the analyses according to the actual values. In the situation that there is insufficient information in a stratum (ie, if there are < 6 subjects or there is no informative event in a stratum), that stratum will be pooled with the smallest adjacent stratum for stratified analyses; the smallest stratum is defined as that stratum having the fewest number of subjects or the fewest number of events in case the former is a tie and the adjacent stratum is defined as a stratum having 2 factors of the 3 at the same level. Data from all sites will be pooled for all analyses. Analyses will be based upon the observed data unless methods for handling missing data are specified. If there is a significant degree of non-normality, analyses may be performed on log-transformed data or nonparametric tests may be applied, as appropriate.

Unless otherwise specified, all analyses will be 2-sided at the 0.05 level of significance.

#### 9.3.2.2. Calculation of Tumor Control and Patient Well-being Variables

Tumor control assessments will be based on standardized IWCLL criteria {[Hallek 2008](#)}, as specifically modified for this study considering the pharmacology of idelalisib and ofatumumab. The individual and composite endpoints of response and progression (considering changes in lymph node area, liver and spleen size, bone marrow, platelet counts, hemoglobin, neutrophil counts, and peripheral blood lymphocyte counts) will be determined. Tumor control will be documented at each assessment by response category (eg, CR, PR, SD, definitive PD, NE, ND) as defined for each response parameter, SPD value, percentage change in SPD values from baseline or nadir, date that response is first documented, date that response is confirmed, and date of definitive CLL progression.

The date of definitive CLL progression will be the timepoint at which progression is first identified by relevant objective radiographic or laboratory data. Where imaging data are available, these data will supersede physical examination data in determining tumor status. For purposes of analysis, subjects who have only physical examination evidence of definitive disease progression that is not confirmed by CT/MRI will be considered to have progressed at the time of the physical examination finding. Because of the characteristic redistribution lymphocytosis that expected with PI3K $\delta$  inhibition, lymphocyte count will be ignored in the evaluations of progression.

Changes in tumor status as provided by the investigator and changes in tumor status as adjudicated by the IRC (see Section [10.4.2](#)) will be described. The findings of the IRC will be considered primary for analyses of PFS and other tumor control endpoints.

The following censoring conventions will be applied:

- PFS: Data from surviving, non-progressing subjects will be censored at the earliest of the time of initiation of antitumor treatment other than the study treatment or the last time that lack of definitive CLL progression was objectively documented. Data from subjects who have CLL progression or die after  $\geq 2$  consecutive missing tumor assessments will be censored at the last time prior to the missing assessments that lack of definitive CLL progression was objectively documented.

- DOR: Data from surviving, non-progressing subjects will be censored at the earliest of the time of initiation of antitumor treatment other than the study treatment or the last time that lack of definitive CLL progression was objectively documented.
- OS: Data from surviving subjects will be censored at the last time that the subject was known to be alive.

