#### **3.3. Primary Endpoint**

- Progression-free survival (PFS) – defined as the interval from randomization to the earlier of the first documentation of definitive disease progression or death from any cause; definitive disease progression is CLL progression based on standard criteria, other than lymphocytosis alone

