### **5.9. Discontinuation from Study**

Subject study participation may be ended due to any of the following reasons:

- Disease progression (confirmed by the IRC)
- Withdrawal of consent
- Initiation of other anticancer therapy
- Physician's decision to remove the subject from the study
- Pregnancy
- The subject is lost to follow-up
- Death
- Discontinuation of study by the Sponsor, a Regulatory Agency, or an IRB or EC

Subjects who permanently discontinue study drug(s) for a reason other than disease progression (as determined by the IRC) shall continue with assessments per the schedule of procedures until disease progression or until study participation is ended.

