### 7.3. Timing of Assessments

During screening, clinical and imaging-based tumor assessments should be performed within the specified screening period. Clinical tumor assessments should be performed at each designated clinical visit (see [Appendix 7](#)). On-study CT/MRI tumor assessments should be performed as indicated in [Appendix 7](#), until ~129 events have been observed in the study population. An end-of-study CT/MRI tumor assessment should be performed unless the subject already has radiographic confirmation of disease progression  $\leq 4$  weeks prior. If a subject permanently discontinues study drug prior to objective documentation of CLL progression, investigators should continue further follow-up according to the protocol specified schedule until CLL progression is documented by the central IRC.

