#### **9.4.1.1. Primary and Supportive Analyses of the Primary Endpoint**

For the primary efficacy analysis, the difference in PFS between the treatment arms will be assessed in the ITT analysis set using Kaplan-Meier methods and the stratified log-rank test, adjusted for the stratification factors. Medians, ranges, the proportion of subjects who are progression-free at 24 and 48 weeks from randomization (based on Kaplan-Meier estimates), hazard ratios and corresponding 95% CIs (as calculated using a Cox proportional hazards regression model) will be presented.

The following exploratory sensitivity analyses will be performed:

- PFS will be compared between the treatment arms in the ITT analysis set using Kaplan-Meier methods and an unstratified log-rank test.
- PFS will also be compared between treatment arms in the PP analysis set using Kaplan-Meier methods and a stratified log-rank test.
- PFS will be further analyzed by censoring data from surviving, non-progressing subjects only at the last time that lack of definitive CLL progression was objectively documented. An additional worst-case sensitivity analysis will be performed in which surviving, nonprogressing subjects who are lost to follow-up are categorized as having an event at the time of the last known CLL tumor status assessment if they were in Arm A and are categorized as censored at the time of the last known CLL tumor status assessment if they were in Arm B. These analyses will be performed in the ITT analysis set using Kaplan-Meier methods and the stratified log-rank test.

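### The primary PFS censoring rule lets a later outcome decide whether time after new antitumor treatment counts; this pulls each arm's curve down and shifts the hazard ratio if the arms start new treatment at unequal rates

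*Protocol*

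**What the plan says.** Section 9.3.2.2 gives two PFS censoring sentences. The first reads: "Data from surviving, non-progressing subjects will be censored at the earliest of the time of initiation of antitumor treatment other than the study treatment", with the last objective documentation of no progression as the alternative date. The second concerns observed events. It covers "Data from subjects who have CLL progression or die after" two or more "consecutive missing tumor assessments will be censored at the last time prior to the missing assessments". It does not mention new treatment.

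Section 3.3 defines PFS as "defined as the interval from randomization to the earlier of the first documentation of definitive disease progression or death from any cause", with no exception for events after new treatment. The duration-of-response bullet in 9.3.2.2 repeats the condition: "DOR: Data from surviving, non-progressing subjects will be censored".

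Three other places determine which later events are seen:
- Section 7.3 says that, after early stop of study drug, "investigators should continue further follow-up according to the protocol specified schedule until CLL progression is documented by the central IRC".
- Section 5.9 lists "Initiation of other anticancer therapy" among the reasons for which participation may be ended.
- Section 6.2.16 collects survival status and antitumor treatments at annual contacts, but schedules no scans.

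Section 9.4.1.1 adds a sensitivity analysis, labelled exploratory: "PFS will be further analyzed by censoring data from surviving, non-progressing subjects only at the last time that lack of definitive CLL progression" was documented. It drops the new-treatment date for everyone.

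**The concern.** Take two subjects who start the same non-study treatment on the same day, both without progression. One progresses four months later and is an event at that date, with the four months counted at risk. The other is event-free at the data cut and is censored at the treatment start, so none of the later time counts. The rule needs to know the outcome before it can decide whether to censor. The Kaplan-Meier estimate, log-rank test and Cox model all assume that it does not.

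The effect is to keep events after new treatment and discard event-free time after it. The hazard is overstated among starters in either arm. If one arm has more starters, its hazard is overstated more, and the primary comparison moves against it. Unequal rates are plausible: sites know the allocation (Section 2.2), Arm B treatment ends at about Week 24, and idelalisib continues in Arm A. More starts in Arm B would favor Arm A in the test that gates all five secondary endpoints.

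**Working it through.** **Inputs from the protocol (Section 9.5).** 170 and 85 subjects; medians 14 and 8 months; 129 events; power above 0.85; 2-sided 0.05; 12-month accrual with half in the first 60% (7.2 months); minimum follow-up 12 months; 10% loss. **Not in the protocol:** the share starting new treatment before progression. All such rates below are assumptions.

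**The plan's own figure.** Events = (1.960 + 1.036)² / [(1/3)(2/3)(ln HR)²]. HR 8/14 gives 130 after rounding up, with power 0.850 at 129. HR 0.57 gives 128, with power 0.853 at 129. The planned 129 is reproduced, so the event count is not the problem.

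**The mechanism by hand.** A median of 8 months means a hazard of ln 2 / 8 = 0.0866 per month. Follow 100 starters for 8 months after their start, assuming the new treatment does not change the hazard.
- Expected events: 50.
- Time at risk: 50 / 0.0866 = 577 months, of which 50 × 8 = 400 belong to the event-free.
- Rule as written: 50 events over 577 − 400 = 177 months, or 0.282 per month, 3.3 times the true hazard.
- New treatment ignored for all: 50 / 577 = 0.0866, correct. All starters censored: no events and no time after the start, also correct.

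**Simulation under no treatment effect.** 3,000 trials per scenario, median 8 months in both arms, accrual as in 9.5, data cut at 19.2 months, unstratified log-rank test. New-treatment start is independent of prognosis. Rates are the share starting before an event, ignoring the data cut. Ranges cover repeated runs. Simulation standard error near 2.5% is √(0.025 × 0.975 / 3000) = 0.3 points.

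| Starters A vs B | Later events that count | HR | False win for Arm A |
|---|---|---|---|
| 10% vs 25% | all | 0.93–0.94 | 5.7–6.3% |
| 10% vs 25% | within about 4 months of start | 0.95 | 5.0–5.4% |
| 10% vs 25% | deaths within 5.5 months, scans stopped | 0.98–0.99 | about 3% |
| 25% vs 10% | all | 1.06 | 1.2–1.6% |
| 10% vs 10% | all | no shift | nominal |
| 10% vs 25%, either consistent rule | – | 0.99–1.00 | 2.3–3.2% |

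The deaths-only row assumes a death hazard of 0.017 per month. Mean entry is (3.6 + 9.6)/2 = 6.6 months, so mean follow-up at 24 months is 17.4. Then 255 × (1 − e^(−0.017 × 17.4)) = 65, the number of deaths that 9.5 expects. About 2 events per trial leak in. Death hazards of 0.03 to 0.05 give HR 0.96–0.97 and 4.0–4.4%.

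**Under the design effect** (8 vs 14 months, about 10% loss, cut at 24 months), the true HR of 0.57 becomes 0.54 with 10% vs 21% starters, 0.63 with 27% vs 8%, and 0.58 with equal start hazards (19% vs 15% starting). Either consistent rule returns 0.57.

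**The case against.** **The sentence may mean progression-free when the new treatment starts.** That would be a sound rule, but the text does not say it. The OS bullet in the same list uses the same kind of phrase for subjects alive at last contact, and the worst-case analysis in 9.4.1.1 uses it for status at the end of follow-up. A programmer following 9.3.2.2 literally would build the outcome-dependent rule.

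**Few later events will be seen.** This carries weight. Section 5.5.1 bars other systemic anticancer therapy on study, 5.9 lets participation end when it starts, and 6.2.16 schedules no scans after that. The missed-assessment rule then removes late deaths. Where participation does end, what leaks in is mainly early deaths, and the shift is small. But ending is permitted, not required, and 7.3 asks for continued follow-up to progression. With 12-week scans, two missed assessments can take up to 24 weeks, about 5.5 months.

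**Imbalance is inferred.** Correct. A reader might infer that the primary test is biased toward Arm A. The protocol gives no start rates, a subject off treatment need not start another, and the reverse imbalance biases the other way.

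**A check exists.** The 9.4.1.1 analysis applies one rule to everyone and would help to expose a material effect. It is exploratory and cannot replace the primary test. It also separates from the primary analysis only where scans continue after new treatment.

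**Censoring details belong in the SAP.** The protocol does not leave this open. It states a rule, and an SAP that follows it inherits the fault.

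**Conclusion.** The rule is wrong as written: whether time after new treatment counts depends on what happens later. Each arm's PFS curve is biased downward as soon as it has starters whose later events are counted. Bias in the HR is conditional. It needs unequal start rates, its direction follows the arm with more starters, and with no true effect it vanishes at equal rates. Under the assumed 10% vs 25%, the size runs from about 0.98–0.99 with about 3% false wins (participation ends, early deaths only) to about 0.93 with about 6% (all later events captured).

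These figures assume that new treatment is unrelated to prognosis and does not alter the hazard, which isolates the effect of the mixed rule. The runs used an unstratified test and a fixed data cut, not the planned stratified test at 129 events.

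Two stronger readings are not supported. False-win rates of 18% to 23% arise only with 39% of Arm B starting new treatment and 14-month medians in both arms, and nothing in the protocol points to 39%. The DOR wording has no type I error consequence, because DOR is exploratory and not among the five tested secondary endpoints. Rating: should fix, with moderate confidence in a material effect on the HR.

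**What to change.** State one rule for every starter in 9.3.2.2, for example: *A subject who starts non-study antitumor treatment before definitive progression is censored at the last assessment before that start, whether or not progression or death follows.* Use the same wording for DOR. Keep the 9.4.1.1 analysis that ignores new treatment as the sensitivity analysis, with all later events counted. Ignoring new treatment for everyone in the primary analysis would be equally consistent; what matters is a single rule. Make the change before any unblinded efficacy analysis.

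The cost is one sentence and some events. If participation ends at new treatment, about 2 events per trial leave the count. If every later event were captured, the 24-month simulation with 10% vs 21% starters loses 156 − 139 = 17 events. The remaining 139 still exceed the planned 129, and power is 0.88 against the planned 0.85.
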